Study Description	This is a single-site, parallel-arm double-blind randomized controlled pilot trial (N=12) of 0.5mg/kg oral ketamine vs. 0.5mg/kg intramuscular ketamine, each administered as a single dose, in combination with 4 sessions of Meaning and Purpose therapy (MaP), for adults diagnosed with stage 3 or 4 gastrointestinal (GI) cancers (i.e., primary pancreatic, colorectal, hepatocellular, biliary, and gastro-esophageal cancers) who have moderate-to-severe demoralization. The combination of ketamine and Meaning and Purpose therapy will be referred to as K-MaP.			
MaP is a brief, existential behavioral intervention. It is a form of talk therapy designed to help patients cope with demoralization through review of the patient's value and worth, their key relationships, and sources of fulfillment and meaning in life [1]. Participants will have sessions of MaP before drug administration, and 2 sessions after administration. The expected study duration from enrollment to stu completion is up to 63 days for each participant.				
	Demoralization is a clinically significant and measurable form of existential distress characterized by poor coping and a sense of helplessness, hopelessness, and a loss of meaning and purpose in life [2, 3]. Demoralization will be measured by Demoralization Scale-II (DS-II), a validated measure [4]. The scale includes 16 items, the total score range is 0-32, and a score of 10 or higher indicates moderate-to-severe demoralization [4, 5]. DS-II will be assessed at baseline, after 2 sessions of MaP but before ketamine, and then 1, 2, and 5 weeks after ketamine. A change in the DS-II of at least 2 points has been considered clinically meaningful in palliative care patients and will be used as a minimum point reduction indicative of efficacy [4].			
Phase of Study	Pilot			
Investigational Products Ketamine				
Study population	Adult stage 3 and 4 GI cancer patients with moderate to severe demoralization.			
Primary Objective	To assess the feasibility of Meaning and Purpose therapy combined with ketamine (K-MaP) in demoralized patients.			

Pilot Study - Ketamine Page 3 of 55

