3.7 Duration of Follow Up

Participants will be followed for 35 days (+/- 2 days) after treatment with ketamine (on Day 0/Visit 4) or removal from the study, whichever occurs first. Participants removed from the study for unacceptable treatment- or study-related adverse event(s) will be followed until resolution or stabilization (as determined by the investigator), whichever occurs first.

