7.3 Prohibited Medications

The medications below may not be used during the study. If participants require these medications, they will be taken off-study (except for when anxiolytics as rescue medications ar used during the ketamine medication visit on Day 0/Visit 4).

- Anxiolytics, as needed
- Lithium

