9.1 Sample Size Considerations

9.1.1 Sample Size and Power Estimate

No formal power analysis was conducted, and no formal tests of efficacy will be conducted. This N=12 pilot study has a sample size sufficient for assessing the feasibility and preliminary safety of a novel behavioral-pharmaceutical intervention, at two different dose levels and routes of administration of the study drug.

If the 0.5mg/kg PO dose of ketamine is well-tolerated (i.e., zero treatment-related SAEs) and demonstrates mean clinical improvement in demoralization assessed by DS-II that endures beyond 7 days post-drug, then this would suggest a fully powered study is warranted using the 0.5mg/kg PO dose.

If the 0.5mg/kg IM dose of ketamine is well-tolerated (i.e., zero treatment-related SAEs) and demonstrates mean clinical improvement in demoralization assessed by DS-II that endures beyond 7 days post-drug, then this would suggest a fully powered study is warranted using the 0.5mg/kg IM dose.

If the either dose is well-tolerated and fails to demonstrate mean clinical improvement in demoralization assessed by DS-II that endures beyond 7 days post-drug, then this would suggest that the dose is an appropriate control for other psychoactive investigational drugs whose clinical effects are expected to have greater durability.

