9.2.2 Primary Analysis (or Analysis of Primary Endpoints)

The primary objective of this pilot study is to assess the feasibility and preliminary safety of administering Meaning and Purpose therapy combined with oral vs. intramuscular ketamine (K-MaP) in demoralized patients with stage 3 or 4 GI cancers (i.e., pancreatic, colorectal, hepatocellular, biliary, or gastro-esophageal). Pre-determined criteria for success of feasibility include:

- A recruitment rate of 50% among referred/screened participants and those ultimately found to be fully eligible and enrolled in the study.
- Completion rates of (i) 75% for participation in 4 Meaning and Purpose therapy sessions and (ii) 80% of 5 on-study DS-II assessments (Visits 1, 4, 6, 8, and 9), in addition to receipt of ketamine.
- Qualitative assessment of clinician fidelity to manualized K-MaP intervention.
- Qualitative assessment of acceptability of the intervention and assessments by participants at the end of the study, with at least 60% of included participants completing this assessment.

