Secondary Objective #2: To assess the magnitude and durability of improvement from randomization in psychosocial distress associated with K-MaP, we will measure mean trends in patient-reported outcomes (DS-II, PHQ9, GAD7, FACIT-PAL-14 scores) in each study arm from baseline visit (Day -28 to -7) to post-ketamine (on Days 7, 14, and 35). In addition, we will calculate the proportion of participants per arm who no longer meet criteria for moderate-to-severe demoralization (i.e., DS-II > 10) post-ketamine. We will also measure mean trends in clinician-rated outcomes (CGI-S, DI, and GRID-HAMD-6 scores) per arm as above. ANCOVA models of follow-up endpoints as a function of study arm, adjusted for endpoints at baseline and randomization, will be conducted [110]. ANCOVA results will be presented graphically via mean trends per arm overlaid on individual trends, and via the mean (95% CI) difference between arms at Day 35. Cohen's d will be calculated at each follow-up time to estimate effect sizes. Any missing data will be estimated through the use of single imputation with baseline observations carried forward.

Secondary Objective #3: We will evaluate BPI-SF scores analogously to DS-II scores.

Secondary Objective #4: We will evaluate opioid analgesia use analogously to DS-II scores.

Secondary Objective #5: We will be using pair t-tests to measure mean changes in MAIA-2 scores in each study arm from prior to ketamine administration (on Day 0) to post-ketamine (on Day 7).

Secondary Objective #6: To assess how participants' subjective experiences with ketamine may be related to clinical outcomes, subjective reports of each participant's ketamine experience (videorecorded from Day 0) will be transcribed, inductively coded, and qualitatively analyzed to identify phenomenological content. In addition, participant MEQ and CEQ scores, which provide summary measures of the intensity of ketamine's acute effects, will be evaluated for potential correlation with trends in DS-II, BPI-SF, and opioid use.

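### A missing follow-up score is replaced by the pre-therapy Visit 1 score, so an arm's mean change can be wrong in either direction when participants leave

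*Combined protocol and SAP*

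**What the plan says.** Secondary Objective #2 in section 9.2.3 concerns "improvement from randomization in psychosocial distress associated with K-MaP". The same paragraph plans mean trends "in each study arm from baseline visit (Day -28 to -7) to post-ketamine (on Days 7, 14, and 35", and its ANCOVA adjusts for the baseline score and the randomization score as two separate covariates. The missing-data rule is: "Any missing data will be estimated through the use of single imputation with baseline observations carried forward". Pain and opioid use are to be analysed in the same way. No sensitivity analysis is planned.

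The calendar in section 6.1 places both pre-ketamine MaP sessions between Visit 1 and Day 0, and its DS-II footnote confirms a DS-II at Visit 4 before ketamine.

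Section 3.7 follows participants for 35 days after ketamine "or removal from the study, whichever occurs first". Section 7.3 lists as-needed anxiolytics and lithium and says: "If participants require these medications, they will be taken off-study", with an exception for anxiolytics used as rescue on Day 0. Section 9.2.1 analyses everyone who received ketamine.

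Section 9.1.1 recommends a powered study for an arm that has no treatment-related serious adverse event and "demonstrates mean clinical improvement in demoralization assessed by DS-II that endures beyond 7 days post-drug". An arm that is tolerated without such improvement is suggested as a control condition. The abstract says that a DS-II change of at least 2 points "will be used as a minimum point reduction indicative of efficacy".

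**The concern.** A dosed participant with no follow-up score remains in the arm mean with a value measured before any therapy. Their change from randomization becomes the Day 0 score minus the Visit 1 score, whatever happened after ketamine. Any Day 0, 7 or 14 score they gave has no influence on the value filled in.

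Loss need not be unrelated to outcome. A participant whose distress rises enough to need an as-needed anxiolytic is taken off study, and section 3.7 then appears to end assessment. The worsening goes unrecorded and the participant is returned to the Visit 1 level.

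What is at stake is the per-arm DS-II mean. With 6 participants per arm, each missing score carries one sixth of the weight in the figure that informs the next-step reading in section 9.1.1.

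**Working it through.** The documents give no loss rate, SD, correlation or effect size, and section 9.1.1 says that no power analysis was done. There is therefore no planned figure to reproduce. Arm size (6), the imputation rule and the 2-point minimum come from the documents; everything else is assumed.

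**Error in the mean.** Let k of 6 scores be missing. The arm's mean score is wrong by

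k/6 × (leavers' average Visit 1 score − their average true score).

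Let g be the fall from Visit 1 to Day 0, and t the leavers' true fall from Day 0. Then Visit 1 minus true score is g + t, and the reported mean fall is wrong by −(k/6)(g + t). It is right only if leavers really returned to their Visit 1 level. Examples:

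- g = 2, t = 2, one missing: −(1/6)(4) = −0.67 points.
- g = 0, t = −4 (worsening), one missing: −(1/6)(−4) = +0.67 points.

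**Chance of showing a 2-point fall.** Assume SD 5 at each visit, correlation 0.7, a true 3-point fall from Day 0, and loss unrelated to outcome. The SD of an individual change is 5 × √(2 × 0.3) = 3.87.

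- *Counted from Day 0:* mean fall = [3(6 − k) − kg]/6, SE = 3.87/√6 = 1.58.
- *Counted from Visit 1:* mean fall = (6 − k)(3 + g)/6, SE = 3.87 × √(6 − k)/6, because an imputed participant contributes exactly zero.

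The chance is Φ[(mean fall − 2)/SE].

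| Reference visit | Fall before Day 0 | Reported mean fall, 0/1/2 missing | Chance of at least 2 points |
|---|---|---|---|
| Day 0 | 0 | 3.0 / 2.5 / 2.0 | 74 / 62 / 50% |
| Day 0 | 2 | 3.0 / 2.2 / 1.3 | 74 / 54 / 34% |
| Visit 1 | 0 | 3.0 / 2.5 / 2.0 | 74 / 64 / 50% |
| Visit 1 | 2 | 5.0 / 4.2 / 3.3 | 97 / 93 / 85% |

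For SD 4 to 7 and correlation 0.5 to 0.8, the SE from Day 0 runs from 4 × √(0.4/6) = 1.03 to 7 × √(1/6) = 2.86. Over both early-fall cases the Day 0 chances are then 64–83% with none missing, 52–69% with one and 26–50% with two.

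**Loss that depends on outcome.** Suppose two leavers end 8 points worse than they otherwise would, a change of 3 − 8 = −5 each. The true arm mean fall is (4 × 3 − 2 × 5)/6 = 0.33. With complete collection, the chance of showing 2 points from Day 0 is Φ[(0.33 − 2)/1.58] = 15%. Baseline carried forward reports 2.0 (g = 0) or 1.3 (g = 2), giving 50% or 34%. In simulation, a mixed model on the observed scores alone showed 2 points 71% of the time, because it assumes that the leavers resemble those who stayed.

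**The case against.** Several stronger readings are tempting, and the documents do not support them.

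- *Section 9.1.1 is a 2-point test of change from randomization.* It names neither a reference visit nor a margin. The 2 points come from the abstract, and section 9.2.3 also describes trends from Visit 1. Counted from Visit 1, the rule is ordinary zero-change carry-forward.
- *Choosing Visit 1 over Day 0 is always damaging.* With no fall before Day 0, the two choices give the same 50% with two missing. Section 1.1 cites a MaP pilot, in patients not selected for distress, with a pre-post DS-II effect of d = 0.16, so little or no early fall is plausible. The spurious worsening needs an early fall.
- *The plan expects two incomplete participants of 12.* The feasibility criterion, "80% of 5 on-study DS-II assessments (Visits 1, 4, 6, 8, and 9), in addition to receipt of ketamine", is a success threshold and not a forecast. It may mean 80% of participants or 4 of 5 assessments each, and anyone lost before dosing is outside the analysis set.
- *The comparison between arms is seriously distorted.* Equal loss for like reasons creates no false difference, although it shrinks a true one by k/6. Under the same SD and correlation, simulated coverage of the interval for the arm difference averaged about 95% over random splits of the loss.
- *The rule is safely conservative, or a mixed model is simply better.* The leaver example contradicts both.

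Section 3.7 could also be read as 35 days from ketamine or from removal, whichever comes first, and it follows adverse events to resolution. Neither reading schedules DS-II assessments after removal, and any missed visit triggers the imputation anyway.

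It is also fair that no formal efficacy test is planned, that individual trends will be plotted, and that complete data would miss 2 points 26% of the time under these assumptions. What stands is narrower: the filled-in value ignores everything after Visit 1, no analysis shows how much that matters, and assessment may stop for the participants who do worst.

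**Conclusion.** The concern holds at the level of the per-arm means. When scores are missing, the rule misstates an arm's mean change by k/6 times the leavers' gap between Visit 1 and true score, and the direction is not fixed. If improvement is counted from Visit 1, or nothing changes before Day 0, this is the usual dilution. A fall before Day 0 adds spurious worsening to the change from randomization.

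The text of the rule is clear, so confidence in the existence of the error is high. Its size rests on the assumed SD, correlation, early fall, effect and number missing. The estimates are secondary and descriptive. The change is worth making because it is cheap and the arms are small.

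**What to change.** 1. **Section 3.7, first.** Continue the Day 7, 14 and 35 outcome assessments after removal from the intervention unless consent is withdrawn. Do this remotely where needed; section 6 already allows remote questionnaires and ratings. State that being taken off study under 7.3 does not end these assessments, leaving the 7.3 medication rule as it is. State also that the resulting scores estimate outcome regardless of removal.

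2. **Section 9.2.3, only with step 1 in place.**
   - Name Day 0 as the reference for change from randomization.
   - Analyse observed scores with a simple repeated-measures mixed model adjusted for Visit 1 and Day 0 where collected. Random effects models are already planned for vital signs.
   - Report baseline carried forward beside it, and read neither alone.
   - Report numbers missing by arm with reasons, and do not impute scores after death.
   - Give the proportion crossing the DS-II cutoff with its observed denominator.

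The cost is wording in two sections, a few remote questionnaires and one extra model. The risk is that scores after removal are still not obtained. The mixed model's missing-at-random assumption can then mislead more than carry-forward does (71% against 34–50% in the leaver example), so step 2 must not be adopted without step 1.

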Secondary Objectives	 To characterize the preliminary safety and tolerability of K-MaP in demoralized patients with stage 3 and 4 GI cancers. To assess the magnitude and durability of improvement from randomization in psychosocial distress. To assess the magnitude and durability of improvement from randomization in pain. To assess the magnitude of change from randomization in opioid analgesic use. To assess the magnitude and durability of change from randomization in interoceptive awareness. 							
Sample Size	12 patients, 6 patients per arm. Arm A: (0.5 mg/kg of ketamine, PO) Arm B: (0.5 mg/kg of ketamine, IM)							
Duration of Study Treatment	Ketamine will be given once on Day 0/Visit 4. Patients will receive MaP therapy 4 times, twice before ketamine administration (Day 0), and twice afterward: 1. Day -13 to -4/Visit 2 2. Day -12 to -1/Visit 3 3. Day 3 (+/- 2 days)/Visit 5 4. Day 11 (+/-2 days)/Visit 7 The duration of treatment for K-MaP therapy (ketamine and MaP) is approximately up to 28 days.							
Duration of Follow up	Patients will be followed up to 35 days (+/-2 days) after ketamine administration.							

Pilot Study - Ketamine Page 4 of 55

Study Schema

Pilot Study - Ketamine Page 5 of 55

List of Abbreviations

AE adverse event

ALP alkaline phosphatase

ALT alanine aminotransferase
AST aspartate aminotransferase

BMP Basic Metabolic Panel

BPI-SF Brief Pain Inventory-Short Form

BUN blood urea nitrogen

CBC complete blood cell (count)

CEQ Challenging Experience Questionnaire

CMP Comprehensive Metabolic Panel

CNS central nervous system

CR complete response

CRF case report form

C-SSRS Columbia Suicidality Severity Rating Scale

CT computerized tomography

CTCAE Common Terminology Criteria for Adverse Events

CTMS Clinical Trial Management System

DFS disease-free survival
DLT Dose-limiting toxicity
DS-II Demoralization Scale II

DSMC Data and Safety Monitoring Committee

DSMP Data and Safety Monitoring Plan

ECG/EKG electrocardiogram

ECOG Eastern Cooperative Oncology Group

FACIT- Functional Assessment of Chronic Illness Therapy Palliative Care 14 Item Version

Pal-14

FDA Food and Drug Administration

FDG Fluorodeoxyglucose

GAD7 General Anxiety Disorder-7

GCP Good Clinical Practice
GFR glomerular filtration rate

HBsAb hepatitis B surface antibody HBsAg hepatitis B surface antigen HBcAb hepatitis B core antibody

HC Ab hepatitis C antibody

Pilot Study - Ketamine Page 6 of 55

List of Abbreviations

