9.1.2 Randomization

Participants will be randomized 1:1, without stratification, in block sizes of 4.

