9.2 Analyses Plans

9.2.1 Population for Analysis

Descriptive analyses will be prepared based on the Modified Intention-to-Treat study populations, including all participants who received a dose of either oral or intramuscular ketamine on Day 0 (at 0.5 mg/kg).

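### MAIA-2 is planned only as a paired t-test within each arm of six; no between-arm estimate is pre-specified, and the named test sits at odds with the plan's own no-testing statement

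*Combined protocol and SAP*

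**What the plan says.** Section 9.2.3, Secondary Objective #5, gives the whole MAIA-2 analysis in one sentence: "We will be using pair t-tests to measure mean changes in MAIA-2 scores in each study arm", from before ketamine on Day 0 to Day 7. No contrast between arms follows.

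For Objective #2 the same section says: "ANCOVA models of follow-up endpoints as a function of study arm, adjusted for endpoints at baseline and randomization, will be conducted". It reports the arm difference with a 95% CI at Day 35. Pain (Objective #3) and opioid use (Objective #4) are to be handled in the same way as DS-II, and mean CEQ scores are compared between arms by ANCOVA.

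On testing in general, Section 9.1.1 says: "No formal power analysis was conducted, and no formal tests of efficacy will be conducted". Section 9.2.1 adds: "Descriptive analyses will be prepared based on the Modified Intention-to-Treat study populations".

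Section 6 and the Study Calendar (Section 6.1) place MAIA-2 at two times only: Day 0 before randomization, and Day 7. Section 2.3 words Objectives 4 and 5 alike, as the magnitude of change from randomization in opioid use and in interoceptive awareness.

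**The concern.** There are three linked problems.

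- **The randomized contrast goes unused for this scale.** Every participant receives ketamine and MaP, so there is no ketamine-free arm. MaP session 3 falls on Day 3 (+/- 2 days), between the two MAIA-2 measurements. Change within an arm therefore mixes ketamine, therapy and the passage of time. Only the comparison of arms removes what the two arms share.
- **Two p-values invite an informal comparison.** With one test per arm, a result below 0.05 in one arm and above it in the other is easily read as a difference between oral and intramuscular ketamine. At six per arm that pattern is common when the true change is the same in both.
- **The plan is inconsistent in its wording.** A paired t-test is a significance test, and MAIA-2 is the only scale given a named significance test of pre-post change.

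At stake is how one secondary scale is interpreted. No go-forward criterion in Section 9.1.1 uses MAIA-2.

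**Working it through.** **Inputs from the documents.** Size: "12 patients, 6 patients per arm" (synopsis). Allocation: "Participants will be randomized 1:1, without stratification, in block sizes of 4" (Section 9.1.2). So 12 / 2 = 6 per arm, in 12 / 4 = 3 complete blocks, and the planned arm size is reproduced. The plan states no power, alpha, effect size, SD or pre-post correlation for MAIA-2, so there is no further figure to reproduce.

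**Assumptions.** Two-sided 5%, in line with the 95% CIs used elsewhere; six analysed per arm; standardized mean change d (mean change / SD of change) from 0 to 1.2; pre-post correlation r from 0.3 to 0.8.

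**Step 1: power of each paired t-test.** This uses the noncentral t distribution with 5 df and noncentrality d x sqrt(6).

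**Step 2: chance that exactly one arm reaches p<0.05 when both have the same true d.** The arms contain different people, so with power p the chance is 2p(1-p). For example, at d = 0.5 it is 2 x 0.171 x 0.829 = 0.283.

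| d | Power per arm | Exactly one arm below 0.05 |
|---|---|---|
| 0 | 5.0% | 9.5% |
| 0.2 | 6.9% | 13% |
| 0.5 | 17% | 28% |
| 0.8 | 36% | 46% |
| 1.0 | 51% | 50% |
| 1.2 | 66% | 45% |

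The ceiling of 2p(1-p) is 50%, reached at p = 0.5, so the rows from d = 0.8 to 1.2 lie close to the worst case. With no true change in either arm, the chance of at least one p<0.05 is 1 - 0.95^2 = 9.75%. A direct between-arm test at 5% would wrongly declare a difference in 5% of trials with equal true change, whatever d is.

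**Step 3: precision of the alternatives (95% CI half-widths).**

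- Within-arm mean change: t(0.975, 5 df) / sqrt(6) = 2.571 / 2.449 = 1.05 SD of change.
- Arm difference in change: t(0.975, 10 df) x sqrt(2/6) = 2.228 x 0.577 = 1.29 SD of change.
- Arm difference by ANCOVA of Day 7 adjusted for Day 0, in raw SD units: t(0.975, 9 df) x sqrt(2/6) x sqrt(1 - r^2). The change-score half-width in the same units is 1.286 x sqrt(2(1 - r)).

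| r | ANCOVA | Change score |
|---|---|---|
| 0.3 | 1.25 | 1.52 |
| 0.5 | 1.13 | 1.29 |
| 0.7 | 0.93 | 1.00 |
| 0.8 | 0.78 | 0.81 |

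The ANCOVA figures ignore chance imbalance in Day 0 scores. ANCOVA is the narrower of the two throughout this range, but both are wide. A two-sample test with six per arm has 80% power only for a standardized difference of 1.80.

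**Step 4: can the data support a comparison?** Yes. A between-arm t-test rebuilt from the two within-arm means and SDs of change matched the test on individual values exactly.

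**The case against.** The best defence is that the analysis fits the objective. Objective 5 asks for the magnitude of change from randomization and names no arm contrast, the hypothesis in Section 2.1 concerns improvement under K-MaP, and the go-forward rules in Section 9.1.1 judge each arm separately. K-MaP is defined as ketamine plus MaP, so a MaP session within the interval belongs to the intervention. This stands in part: a within-arm estimate is a legitimate description and should be kept. It does not explain the missing contrast, because Objective 4 has the same wording and gets the ANCOVA.

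A second defence is that the conflict with Section 9.1.1 is only verbal. The t-tests are there to measure mean changes, with no alpha or decision rule, and the analyses are labelled descriptive. That is fair, and reporting estimates with intervals removes the conflict. Third, the Objective 2 model could not be applied as written, since MAIA-2 has no Visit 1 or Day 35 value. That is true, but a Day 0-adjusted model at Day 7 needs neither.

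A reader might infer more than the documents support:

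- **That the arms cannot be compared on MAIA-2.** Both arms have Day 0 and Day 7 scores. The comparison is omitted, not prevented.
- **That MAIA-2 is treated unlike every other scale.** MEQ and the heartbeat detection task are analysed only by correlation, and C-SSRS has no stated efficacy model. The accurate contrast is with the Objective 2-4 outcomes and CEQ.
- **That the plan intends to compare the two p-values.** It nowhere says so; the risk lies in how the results would be read.

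**Conclusion.** The point holds as a low-severity one. MAIA-2 has only separate within-arm significance tests at a planned six per arm, no between-arm estimate is pre-specified, and naming the tests sits at odds with Section 9.1.1.

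The chance of a misleading one-arm-only result, given equal true change, runs from 9.5% to 50% over the assumed d of 0 to 1.2. Those figures rest on two-sided 5%, six analysed per arm and effect sizes that the documents do not supply. They describe a hazard only if someone contrasts the two p-values.

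The between-arm estimate is better focused but not precise, and it could not rule out sizeable differences in either direction. The primary endpoint, the safety criteria and the go-forward rules are unaffected.

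**What to change.** In Section 9.2.3, Secondary Objective #5, replace the paired t-tests with:

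1. An ANCOVA of Day 7 MAIA-2 on study arm, adjusted for the Day 0 pre-dose MAIA-2 score, reporting the arm difference with its 95% CI.
2. Mean change from Day 0 to Day 7 within each arm with its 95% CI, and no p-values.

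Add that these are estimates only, in line with Section 9.1.1, which can then stand as written.

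The cost is two or three sentences, with no new data, visits or participants. The change is best made before anyone sees results by arm. The price is a wide interval for the arm difference, which should be stated when it is reported.
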